8.1.1. Primary Analysis

The primary efficacy analysis will be an analysis of variance (ANOVA) of the area under the time-corrected endogenous creatinine clearance curve from Day 1 to Day 7 with treatment and site as explanatory variables.

For all patients recruited up to the interim analysis, the primary efficacy analysis will be conducted for the ITT Combined Set at the interim analysis (which is identical to the ITT Part 1 Interim set at the time of the interim analysis) where AUC_{1-7} will be compared between the 3 active treatment groups and placebo. This analysis will be considered in conjunction with the safety data to determine the optimal recAP dose for use in Part 2.

The primary efficacy analysis will be conducted for the ITT Part 2 Set, PP Day 1 – 7 Part 1 and PP Day 1 – 7 Part 2 Set where AUC_{1-7} will be compared between the optimal recAP dose and placebo (for the PP Day 1 -7 Combined Set, each dose of recAP will be compared to Placebo). Also, all doses combined will be compared to Placebo.

Confirmatory testing of the single hypothesis comparing optimal dose with placebo will be based on a closed-testing procedure. This hypothesis will be rejected at the 5% significant level if it and all intersection hypotheses involving it are all rejected at the 5% significance level. The testing strategy used to combine results from Parts 1 and 2 will be a combination test based on the inverse normal method, with the test statistic of the combination test calculated as ([Bauer and Köhne 1994](#)):

$$\sqrt{\frac{n_1}{n}} \Phi^{-1}(1 - p_1) + \sqrt{\frac{n_2}{n}} \Phi^{-1}(1 - p_2)$$

where n_1 and n_2 are the sample sizes per group in interim analysis at Part 1 and in Part 2, respectively, $n = n_1 + n_2$, Φ refers to the standard normal distribution, and p_1 and p_2 are the one-sided p-values from interim analysis at Part 1 and from Part 2, respectively. For the intersection hypotheses, p_1 is the Dunnett adjusted one-sided p-value in Part 1 (for the optimal dose selected), and p_2 is the one-sided unadjusted p-value to compare optimal dose with placebo in Part 2 for all hypotheses.

Results from the primary analysis for interim analysis at Part 1 and for Part 2 will include least square means for each treatment and the difference in least squares means between the treatment groups will also be presented along with the associated 95% CI. P-values will be presented for least square mean treatment differences. The one-sided p-value for the combined analysis will be presented with the sample sizes and one-sided p-values from the interim analysis at Part 1 and at Part 2.

Descriptive statistics for the primary endpoint and mean standardized endogenous creatinine clearance at Day 1 to Day 7 will also be presented in a summary table by

treatment. This will be presented for all four treatment groups for the ITT Combined, ITT part 1 Interim, PP Day 1-7 Part 1, and also for the optimal recAP dose and placebo treatment groups for the ITT Part 2 and PP Day 1-7 Part 2 Sets. Analysis on the PP Set will be used as a supplement to the ITT analysis. The ITT Part 1 Interim Set (for all four treatment groups) will also be produced to help check the assumption of the combined analysis that patients recruited in each part of the study belong to the same overall patient population.

The primary endpoint, AUC_{1-7} , and standardized endogenous creatinine clearance at Day 1 to Day 7 will be listed.

A time-course plot of standardized endogenous creatinine clearance with associated error bars on each day will be presented for the optimal recAP dose and placebo groups. This plot will be repeated three times using different selection criteria for the data based on data imputation and adjudication of creatinine clearance data:

- 1) Including only calculated values (i.e. no imputed values)
- 2) Including all (non-adjudicated) calculated and imputed values
- 3) Including only adjudicated calculated and imputed values

The combined ITT analysis primary endpoint summary and analysis will be repeated as a supportive sensitivity analysis, excluding patients who died before day 8, with SAS[®] output from Part 1 and Part 2 models included on the primary combined analysis output. Additionally, descriptive statistics for the primary endpoint and mean time-corrected endogenous creatinine clearance at Day 1 to Day 7 will be presented in a summary table for the ITT Combined Set by treatment group and subgroup category, defined in [Section 8.1.5](#).

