### **3 Investigational Plan**

#### **3.1 Study Design**

This is a randomized, double-blind, placebo-controlled, 4-arm, parallel-group, proof-of-concept, and dose-finding adaptive Phase 2a/2b study.

Approximately 100 sites will participate in the study; approximately 75 in the European Union and approximately 25 in the United States and Canada. Participating sites will be required to adhere to the Surviving Sepsis Campaign 2012 (Delinger et al 2013) and KDIGO® (Kidney Disease: Improving Global Outcomes) Clinical Practice Guideline for AKI recommendations (KDIGO Acute Kidney Working Group 2012).

A minimum of 290 patients with SA-AKI will be enrolled in the study. The study involves 2 parts (Part 1, Part 2) with an interim analysis between the parts, with continued recruitment during this interim analysis. Of the 290 planned patients, at least 120 patients will enroll in Part 1 and 170 patients will enroll in Part 2 with an estimated 50 patients during the interim analysis. Patients enrolled during Part 1 and interim analysis will be randomly assigned to receive, by 1-hour IV infusion, either placebo (Part 1; n1 = 30) or one of 3 different doses of recAP (Part 1; n1 = 30 in each dosing arm; i.e., 0.4 mg/kg [250 U/kg], or 0.8 mg/kg [500 U/kg], or 1.6 mg/kg [1000 U/kg]) using a 1:1:1:1 allocation ratio. Patients will receive study drug by 1-hour IV infusion once daily for 3 days (Days 1, 2, and 3). The interim analysis on the primary endpoint will be performed on all the data collected after the 120th patient of Part 1 has completed the Day 7 visit of the study to select the dose to be administered in Part 2. The dose chosen will be the optimal dose of recAP on the primary endpoint in Part 1, provided there are no safety issues with that dose as judged by the data monitoring committee (DMC). In Part 2, patients will be randomly assigned to receive, by 1-

[figure not shown]
hour IV infusion, either placebo ( $n_2 = 85$ ) or the dose of recAP ( $n_2 = 85$ ) selected during the interim analysis. Patients recruited during the interim analysis period to the dose selected in Part 2 will form part of the Part 2 populations, but those recruited to the doses that are not selected will be included in the Part 1 population.

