## 7.4 Sample Size Calculations

A sample size of  $n_1 = 30$  patients per treatment group in Part 1 with an additional  $n_2 = 85$  patients recruited to the optimal recAP dose and placebo treatment groups in Part 2 (for a total sample size of  $n = 290$  patients) is planned. Recruitment will continue during the interim analysis so the total number of patients may exceed 290 patients. Patients recruited during this period to the dose selected in Part 2 will form part of the Part 2 populations, but those recruited to the doses that are not selected will be included in the Part 1 population. Custom programmed simulations were performed using SAS software Version 9.2 to determine power and type I error rate of the chosen sample size and design under a number of different dose response scenarios. Each scenario assumed a standard deviation of 49 mL/min for the primary endpoint ( $AUC_{1-7}$ ) with an assumed response of 60 mL/min for the placebo group, and between 60 mL/min (no treatment effect) and 79 mL/min (strong treatment effect) for the recAP dose groups.

Fifty-thousand simulations were performed to show that the 1-sided type I error rate is 2.4% (and hence is well controlled at the 1-sided 2.5% significance level). The power was defined as the probability of rejecting the null hypothesis (of no difference between treatment groups) when 1 or more recAP dose groups have an effective treatment effect, defined as a response of 69.5 mL/min. This was investigated across 7 scenarios with 10 000 simulations performed for each. In the most realistic scenarios (with strong treatment effects, i.e., responses of

79 mL/min for the medium and high recAP dose groups and a varying response of between 60 mL/min and 79 mL/min for the low-dose group) the chosen design achieved power of between 79% and 86%. This dropped to 66% to 67% for other scenarios where only the high recAP dose group had a strong treatment effect.

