### **7.7.1 Analysis of Primary Efficacy Endpoint**

The primary efficacy endpoint is the area under the time-corrected endogenous creatinine clearance curve from Day 1 to Day 7, i.e.,  $AUC_{1-7}$ .

Area under the time-corrected endogenous creatinine clearance curve from Day 1 to Day 7 will be summarized using descriptive statistics and analyzed using an analysis of variance (ANOVA) with treatment and site as explanatory variables. The analysis will be performed separately for Parts 1 and 2: for Part 1,  $AUC_{1-7}$  will be compared between the 3 recAP doses and placebo. This analysis will be considered in conjunction with the safety data to determine

the optimal recAP dose for use in Part 2. For Part 2, the optimal recAP dose will be compared with placebo. Confirmatory testing of the single hypothesis comparing optimal dose with placebo will be based on a closed-testing procedure. This hypothesis will be rejected at level  $\alpha$  if it and all intersection hypotheses involving it are all rejected at local level  $\alpha$ . The testing strategy used to combine results from Parts 1 and 2 will be a combination test based on the inverse normal method, with the test statistic of the combination test calculated as (Bauer and Köhne 1994):

$$\sqrt{\frac{n_1}{n}} \Phi^{-1}(1 - p_1) + \sqrt{\frac{n_2}{n}} \Phi^{-1}(1 - p_2)$$

where  $n_1$  and  $n_2$  are the sample sizes per group in Parts 1 and 2, respectively,  $n = n_1 + n_2$ ,  $\Phi$  refers to the standard normal distribution, and  $p_1$  and  $p_2$  are the p-values from Parts 1 and 2, respectively. For the single hypothesis,  $p_1$  is the unadjusted p-value to compare optimal dose with placebo in Part 1. For the intersection hypotheses,  $p_1$  is the Dunnett-adjusted p-value in Part 1, and  $p_2$  is the unadjusted p-value to compare optimal dose with placebo in Part 2 for all hypotheses.

The difference in least squares means between the treatment groups will also be presented along with the associated 95% CI.

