**Change to or Section Deleted:**

The primary endpoint, **area under the time-corrected endogenous creatinine clearance curve**, was chosen because...

...

Urine and serum creatinine determinations will be performed to enable calculation of time-corrected endogenous creatinine clearance, ~~considered as the primary endpoint~~, at all visits from Day 0 to Day 7, and calculated by the central laboratory. **The measurements from Day 1 to Day 7, inclusive, will be used to calculate the primary endpoint.** Only if reliable urine collection is possible, urine will be collected on Days 14, 21, and 28 for **time-corrected endogenous creatinine clearance** (i.e., patient is in the ICU or hospital).

...

Each scenario assumed a standard deviation of 49 mL/min for the primary endpoint (area under the **time-corrected endogenous** creatinine clearance curve from Day 1 to Day 7 [AUC1-7])...

...

The primary efficacy endpoint, area under the **time-corrected endogenous** creatinine clearance curve from Day 1 to Day 7 (AUC1-7), will be summarized using descriptive statistics and analyzed using analysis of variance with treatment and site as explanatory variables.

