#### 14.2.1.1 Reason:

Addition of new countries and sites projected for the study. Clarification on analysis of patients during interim analysis period.

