#### Change to or Section Deleted:

Approximately ~~50~~ **100** sites will participate in the **study**; ~~approximately 75 in the European Union and approximately 25 in the United States and Canada.~~ **Recruitment will continue during the interim analysis.**

**A minimum of 290 patients with SA-AKI will be enrolled in the study. The study involves 2 parts (Part 1, Part 2) with an interim analysis between the parts, with ~~potentially~~ continued recruitment during this interim analysis. Of the 290 planned patients, at least 120 patients will enroll in Part 1 and 170 patients will enroll in Part 2 with an estimated 50 patients during the interim analysis. Patients enrolled during Part 1 and during the interim analysis will be randomly assigned to receive, by 1-hour intravenous (IV) infusion, either placebo (Part 1;  $n_1 = 30$ ) or one of 3 different doses of recAP (Part 1;  $n_1 = 30$  in each dosing arm; i.e., 0.4 mg/kg [250 U/kg], or 0.8 mg/kg [500 U/kg], or 1.6 mg/kg [1000 U/kg]) using a 1:1:1:1 allocation ratio. Patients will receive study drug by 1-hour IV infusion once daily for 3 days (Days 1, 2, and 3). The interim analysis on the primary endpoint will be performed on all data collected after all the patients the 120th patient of Part 1 has completed the first 7 days in Part 1 Day 7 visit of the study to select the dose to be administered in Part 2. The dose chosen will be the optimal dose of recAP on the primary endpoint in Part 1, provided there are no safety issues with that dose as judged by the DMC. In Part 2, patients will be randomly assigned to receive, by 1-hour IV infusion, either placebo ( $n_2 = 85$ ) or the dose of recAP ( $n_2 = 85$ ) selected during the interim analysis. Patients recruited during the interim analysis period to the dose selected in Part 2 will form part of the Part 2 populations, but those recruited to the doses that are not selected will be included in the Part 1 population.**

## 14.2.2 Change Number 2

Study design section has been amended with regard to inclusion and exclusion criteria.

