4.1. Sample Size

A sample size of $n_1 = 30$ patients per treatment group in Part 1 with an additional $n_2 = 85$ patients recruited to each of the optimal recAP dose and placebo treatment groups in Part 2 (for a total sample size of $n = 290$ patients) is planned. Recruitment will continue during the interim analysis, so the total number of patients will exceed 290. Custom programmed simulations were performed using SAS[®] Version 9.2 (SAS Institute, Inc, Cary, North Carolina) to determine power and type I error rate of the chosen sample size and design under a number of different dose response scenarios. Each scenario assumed a standard deviation of 49 mL/min for the primary endpoint (area under the time-corrected endogenous creatinine clearance curve from Day 1 to Day 7 [AUC₁₋₇]) with an assumed response of 60 mL/min for the placebo group, and between 60 mL/min (no treatment effect) and 79 mL/min (strong treatment effect) for the recAP dose groups.

Fifty-thousand simulations were performed to show that the 1-sided type I error rate is 2.4% (and hence is well controlled at the 1-sided 2.5% significance level). The power was defined as the probability of rejecting the null hypothesis (of no difference between treatment groups) when 1 or more recAP dose groups have an effective treatment effect, defined as a response of 69.5 mL/min. This was investigated across 7 scenarios with 10 000 simulations performed for each. In the most realistic scenarios (with strong treatment effects, i.e., responses of 79 mL/min for the medium and high recAP dose groups and a varying response of between 60 mL/min and 79 mL/min for the low-dose group) the chosen design achieved power of between 79% and 86%. This dropped to 66% to 67% for other scenarios where only the high recAP dose group had a strong treatment effect.

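### The primary ANOVA fits about 100 planned sites separately in each part with no small-site rule, and the 79-86% power is stated without the site assumptions that decide whether it holds

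*SAP*

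**What the plan says.** The primary analysis (SAP 8.1.1) is an ANOVA of the area under the "creatinine clearance curve from Day 1 to Day 7 with treatment and site as explanatory variables". Protocol 7.7.1 adds: "The analysis will be performed separately for Parts 1 and 2". Protocol 3.1 plans the sites: "Approximately 100 sites will participate in the study; approximately 75 in the European Union and approximately 25 in the United States and Canada". Randomisation uses permuted blocks stratified by site, with no block size given. After dose selection the same schedule continues with the dropped codes skipped (Protocol 5.1, SAP 4.2).

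On power, Protocol 7.4 states: "Each scenario assumed a standard deviation of 49 mL/min for the primary endpoint". The placebo mean is 60 mL/min and the active means run from 60 to 79. In the three scenarios with 79 mL/min on the medium and high doses, "the chosen design achieved power of between 79% and 86" per cent; where only the high dose works strongly, power is 66-67%. Neither Protocol 7.4 nor SAP 4.1 mentions a site term, a number of sites, a between-site variance or an enrolment pattern.

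The rank-based fallback in SAP 8.1.3 keeps site. The only rule for removing site is in SAP 8.2.1, for the logistic model of RRT incidence.

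**The concern.** If all 100 sites recruit in both parts, the average is 120/100 = 1.2 patients per site in Part 1 and 170/100 = 1.7 in Part 2. With 50 sites it is 2.4 and 3.4. When site is a fixed effect, a site with one patient, or with patients in only one arm, adds nothing to the treatment contrast, and each site costs a degree of freedom. Against this, fitting site removes any between-site variance from the error term. Power can therefore fall or rise, and the documents do not give what is needed to say which.

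The figure matters because a non-significant result would be read against 79-86% power, and the key secondary test is formal only if the primary test succeeds.

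**Working it through.** **Inputs from the documents.** 30 per arm in Part 1 and 85 per arm in Part 2; SD 49; means 60 and 79; one-sided 2.5%; inverse normal weights √(30/115) = 0.511 and √(85/115) = 0.860; Dunnett-adjusted p-value in Part 1; futility stop if all three one-sided p-values exceed 0.8.

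**Assumed, because the documents do not say.** Blocks of 4; sites recruiting per part; random or skewed enrolment (skewed = gamma site weights, shape 1); between-site variance of 0, 10 or 20% inside the total SD of 49; site effects shared across parts.

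**1. The plan's own figure.** A two-stage simulation without site (2,500 trials per setting, Monte Carlo SE 0.6-1.0 point) gives 79/82/86% for low-dose means of 69.5/60/79, against the stated 79-86%. A separate run gave 79/81/85%, type I error 2.3% (stated 2.4%) and 66-68% in the high-dose-only scenarios (stated 66-67%).

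**2. Mechanism by hand, for a single dose without selection.** The expected Z is 19/(49√(2/30)) = 1.502 in Part 1 and 19/(49√(2/85)) = 2.528 in Part 2. Combined: 0.511 × 1.502 + 0.860 × 2.528 = 2.940, so power = Φ(2.940 − 1.96) = 83.7%.

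Now multiply each part's Z by the square root of the simulated share of information that remains once site is fitted:
- 100 sites in both parts, random enrolment (54% and 72% retained): 0.511 × 1.502 × √0.54 + 0.860 × 2.528 × √0.72 = 2.408, power 67%.
- 50 sites in both parts, random enrolment (79% and 90% retained): 2.743, power 78%.
- The same 50 sites with 10% of the variance between sites: 2.743/√0.9 = 2.892, power 82%, close to the 83.7% without site.

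Residual degrees of freedom (random/skewed) are 47/62 in Part 1 and 87/106 in Part 2 with 100 sites, and 71/81 and 121/130 with 50.

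**3. Planned model, full simulation.** Power (%) for low dose 69.5/60/79, Part 2 N = 170. The last column is the change against 79/82/86.

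| Sites, Part 1 / Part 2 | Site variance | Random enrolment | Skewed enrolment | Change (points) |
|---|---|---|---|---|
| 100 / 100 | 0% | 60/64/70 | 67/70/76 | −19 to −10 |
| 100 / 100 | 10% | 65/65/72 | 72/76/80 | −17 to −6 |
| 100 / 100 | 20% | 72/72/79 | 77/78/83 | −10 to −2 |
| 50 / 100 | 0% | 68/71/75 | 71/73/79 | −11 to −7 |
| 50 / 100 | 10% | 71/75/79 | 76/78/82 | −8 to −3 |
| 50 / 100 | 20% | 77/78/84 | 80/82/86 | −4 to +1 |
| 50 / 50 | 0% | 72/76/81 | 75/75/83 | −7 to −3 |
| 50 / 50 | 10% | 78/81/84 | 78/81/85 | −2 to −1 |
| 50 / 50 | 20% | 82/83/88 | 83/86/89 | +1 to +4 |

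**4. Block size.** With blocks of 8, 100 evenly enrolling sites and no site variance, power was 57% (low dose 60) and 63% (low dose 79), against 81% and 85% without site in the same run. The losses are 24 and 22 points.

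**5. Interim-period patients.** Adding 25 of the estimated 50 gives Part 2 N = 195. With skewed enrolment and 10% site variance, power is 76/79/82 (100/100 sites), 79/83/87 (50/100) and 83/86/89 (50/50). Only the first is below the stated 79/82/86, by 3-4 points.

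**6. Type I error.** Over nine null settings (8,000 trials each, SE 0.17 point) the one-sided rate was 2.0-2.8% for the planned model, 2.2-2.8% with random site in Part 2 and 2.1-2.9% with small-site pooling in Part 2.

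**The case against.** The strongest objection is that no error in the power figure has been shown. A reader might infer from the site-free match that site was omitted from the sponsor's simulation. The documents do not support that: 50 sites in both parts with 10% site variance gives 78/81/84 or 78/81/85, which cannot be told apart from 79/82/86 at this Monte Carlo precision. About 50 sites was the planned number before Amendment 2, and the SD assumption already stood in Amendment 1. That history serves only to choose plausible site inputs and is not evidence of a mistake. This objection stands in full.

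A reader might also take the top rows of the table as the trial's real power, so that a true 79 versus 60 effect is missed in 24-40% of trials. That needs 100 sites recruiting in both parts and no between-site variance, the harshest layout at block size 4. The documents give neither input.

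Three more points have weight. Fitting the stratification factor is a coherent choice. The RRT rule answers model-fitting failure, which an ANOVA does not suffer in the same way, so its absence from SAP 8.1.1 is not an inconsistency. And SAP 4.1 says: "Recruitment will continue during the interim analysis, so the total number of patients will exceed 290". Patients on placebo or the selected dose during the interim join Part 2 (SAP 4), although the text does not settle whether they add to the 170.

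What survives is that the planned model can cost appreciable power at the planned site number, and that the power section does not let a reader judge whether it does.

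**Conclusion.** The concern holds as a conditional one. With blocks of 4 and 0-20% site variance, the change against 79/82/86 is a loss of 2-19 points with 100 sites in both parts, between a 1-point gain and an 11-point loss with 50 then 100 sites, and between a 4-point gain and a 7-point loss with 50 in both. These ranges are not bounds, as the block-size-8 result shows. The shortfall shrinks if interim-period patients add to the 170. The issue is possible lost efficiency and an incomplete power statement; bias and type I error inflation are not in question. Severity: minor to moderate.

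**What to change.** 1. Restate power under the model to be fitted, as a range over stated assumptions on sites per part, enrolment pattern, block size and between-site variance. Say whether site was in the original simulation.
2. Before final unblinding, and on blinded site counts, pre-specify that in the Part 2 ANOVA sites below a set number of patients (for example fewer than 4) are pooled within country or region. A random site effect fitted by REML, with the degrees-of-freedom method named, is an alternative. Record the choice in SAP section 12 as a change from Protocol 7.7.1.
3. Keep the interim Part 1 p-value as produced (SAP 8.1.4 describes the interim as already done). Refit Part 1 with the new model only as a sensitivity analysis.

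The cost is SAP wording and one re-run of the simulation, with no extra patients. Pooling recovered 2-11 points (100/100 sites), 1-8 (50/100) and 0-2 (50/50), assuming 10 countries. Random site recovered 4-12, about 4-9 and 1-4. Neither lost more than 0.3 points against the planned model in any setting. The downsides are that the two parts then handle site differently, that pooling assumes effects shared within country or region while random site assumes exchangeable sites, and that the gain is small if only about 50 sites recruit.
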